6.2.2 Safety

- The Research Associate will remain at the patient's bedside for the first 10 minutes after medication administration, during local infiltration and from the time of initial incision until dressing application
- At 15 minute intervals after intranasal medication administration of the study medication, the RA will measure and record vital signs (including SaO₂ by pulse oximeter).
- No further monitoring will be performed after 120 minutes.

6.2.2.1 Adverse Events Definition and Reporting

Any adverse events will be managed at the discretion of the treating provider.

All vital signs that fall below the thresholds described above will be reported to the Data Safety Monitoring (DSM) individual and included in the annual progress report to the IRB. The DSM monitoring will consist of [name], MD, the director of the Moses ED and [name], Ph.D, head of the Division of Research of the Department of Emergency Medicine. They will meet every month with the PI to 1) monitor adverse events and develop strategies to minimize these; and 2) monitor recruitment and enrollment.

6.3 Study Procedures

- The RAs and attending physicians will identify eligible patients. To participate, patients must have capacity to provide informed consent.
- The healthcare provider and the RA will describe the study to eligible patients and obtain patient consent.
- The RA will weigh patient, obtain a baseline NRS pain score and initial vital sign information.
- The RA will have the nurse remove the next study packet from the PYXIS, which will be either 4 mL vial containing either fentanyl 50mcg/mL or sterile water. The contents will be concealed by the research pharmacist.
- Patients will receive the blinded study medication either 2 mcg/kg of fentanyl or 0.04 mL/kg of sterile water (max 4mL) weight based and rounded to the nearest 10kg (excluding patients > 100kg to prevent excessive opioid dosing) via an atomizer syringe (half of total volume in each nostril) 15 minutes prior to local infiltration
- The RA will prompt the treating provider 15 minutes after local infiltration to ensure prompt treatment during an optimal systemic and local analgesic window. If the I&D has not been initiated within 30 minutes of INF administration the patient will not be included in the analyses due to concern for considerable tapering of INF analgesia (accounted for in sample size calculation).
- At 15 minute intervals following the intranasal medication administration, the RA will obtain vital signs (including SaO₂ by pulse oximeter), and record incidence of side effects and adverse events.
- The RA will record all medications administered in the ED and the time of their administration from the chart and the treating attending physician.

- RAs will record the time of each pertinent procedural step: Initial NRS collection time, location of abscess, size of abscess (cm), complexity of procedure (simple: requires minimal blunt instrumentation, moderate: requires more than minimal blunt instrumentation, complex: requires more than moderate instrumentation), use of packing (yes/no), study medication administration time, local infiltration time, incision/instrumentation/packing /irrigation time, dressing application time and discharge time.

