4.1 Hypothesis

2 mcg/kg of INF will provide better pain control than placebo when used as an adjunct to conventional local anesthesia to reduce overall pain of the procedure in adult ED patients undergoing lidocaine infiltration and subsequent abscess incision and drainage, as measured on a 0-10 pain scale.

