5.2 Outcome Variables

5.2.1 Primary Outcome Variables

The primary outcome is the between group difference in numerical rating scale (NRS) pain scores for overall pain of the procedure, defined as anesthetic infiltration plus abscess incision and drainage, including breaking up of adhesions, irrigation, and packing as indicated. The time for obtaining this primary NRS endpoint will be standardized as the time of completion of application of the bandage. The NRS is a reliable and validated measure of pain intensity ranging from 0 – no pain, to 10 – worst pain imaginable.

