6.4.2 Sample Size Considerations

A sample size of 49 patients will support the primary outcome, based on the observed SD of 3.2, if the between group difference is no less than 2.8. This was calculated based on the following parameters: alpha = 0.05 and power = 0.8. Although smaller differences may be clinically relevant, a between-group difference of 2.8 is generally regarded as a robust difference.

We used nQuery Advisor version 7.0 (Los Angeles, CA) to calculate the sample size.

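### Section 6.3 times the prompt to start I&D at minute 30 after study drug, the same minute at which an unstarted patient is dropped from the analyses

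*Combined protocol and SAP*

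**What the plan says.** Three timing rules stand together in section 6.3.

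- Study drug is sprayed intranasally: "half of total volume in each nostril) 15 minutes prior to local infiltration".
- The reminder comes later: "The RA will prompt the treating provider 15 minutes after local infiltration to ensure prompt treatment". The stated aim is to treat while both the systemic and the local drug are working.
- The limit follows directly: "If the I&D has not been initiated within 30 minutes of INF administration the patient will not be included in the analyses". The reason given is waning of the intranasal analgesia, and the loss is said to be allowed for in the sample size.

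Section 6.2.2 has the RA at the bedside for the first 10 minutes after dosing and then "during local infiltration and from the time of initial incision until dressing application". It also has vital signs taken every 15 minutes from study drug. Sections 5.2.2 and 6.2.1 require a pain score immediately after infiltration.

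Section 6.4.2 sets the size: "A sample size of 49 patients will support the primary outcome, based on the observed SD of 3.2". It uses a difference of 2.8, alpha 0.05 and power 0.8. It states neither the sidedness of alpha nor a rate of loss.

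**The concern.** The prompt is the only written step that protects against a late start, and on schedule it arrives at the moment the limit expires. The two rules also run on different clocks: the prompt is counted from infiltration and the limit from study drug. A late infiltration therefore moves the prompt but not the limit.

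At stake are patients who have been randomised and dosed, and who could be dropped from the primary analysis although the RA followed the procedure exactly.

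**Working it through.** **1. What starts the 30-minute test.** If infiltration counted as the start of I&D, the problem would disappear, because infiltration is due at minute 15. The plan treats it as a separate, earlier step:

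- The hypothesis in 4.1 describes patients "undergoing lidocaine infiltration and subsequent abscess incision and drainage".
- Section 5.2.1 has the overall procedure "defined as anesthetic infiltration plus abscess incision and drainage".
- Section 5.2.2 scores pain separately after each step, and 6.3 records their times separately.

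The prompt sentence does not name I&D. However, it comes after infiltration, refers to the local anaesthetic window and is followed at once by the I&D limit, so the start of I&D is the only sensible reading.

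**2. The clock, from 6.3 (minutes after study drug).**

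| Event | On schedule | Infiltration 3 minutes late |
|---|---|---|
| Study drug | 0 | 0 |
| Infiltration | 15 | 18 |
| Prompt | 15 + 15 = 30 | 18 + 15 = 33 |
| Limit for I&D start | 30 | 30 |
| Margin after prompt | 30 − 30 = 0 | 30 − 33 = −3 |

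In general, if infiltration occurs at minute T, the margin is 30 − (T + 15) = 15 − T. It is zero at T = 15 and negative for any later T.

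**3. The plan's sample size.** Inputs from 6.4.2 are difference 2.8, SD 3.2, alpha 0.05 and power 0.8. The independent-group t-test is from 6.4.3.1. Two-sided alpha and equal allocation are assumed. The standardised difference is 2.8 / 3.2 = 0.875. The two-sided t-test needs 21.5 per arm, so 22 per arm or 44 in total. Allowing for 10% loss, 44 / 0.9 = 48.9, which rounds up to 49. The stated figure can thus be reproduced as a total, but the 10% is inferred and appears nowhere in the plan.

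**4. How many exclusions 49 can absorb.** Power is from the noncentral t distribution with n1 + n2 − 2 degrees of freedom and noncentrality 0.875 × √(n1·n2 / (n1 + n2)). For 25/24 this is 0.875 × √(600/49) = 3.06.

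| Excluded of 49 | Analysed (arms) | Power, two-sided 0.05 |
|---|---|---|
| 0 | 49 (25/24) | 0.85 |
| 5 (10.2%) | 44 (22/22) | 0.81 |
| 5, all from one arm | 44 (25/19) | 0.802 |
| 6 (12.2%) | 43 (22/21) | 0.7997 |
| 10 (20.4%) | 39 (20/19) | 0.76 |
| 15 (30.6%) | 34 (17/17) | 0.70 |

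If alpha were one-sided at 0.05, 34 analysed (17/17) would give 0.803, so 49 − 34 = 15 exclusions could be absorbed when losses are balanced. These are tolerances, not expected losses.

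**The case against.** The strongest reply is that nothing obliges the provider to wait. Section 6.3 sets no minimum interval between infiltration and incision, so on schedule I&D may start at any time from minute 15 to minute 30, and a start at minute 30 counts. The prompt can be read as a last call. The plan says late starts are allowed for, and 49 exceeds the 44 that a two-sided test needs. All of this stands. It means that no loss can be predicted, but a last call made when time has run out still does not do its job.

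A reader might infer that the patient goes unattended between infiltration and the limit, since bedside presence lapses and vital signs fall at minutes 15 and 30. The documents do not support that. The RA is present during infiltration and a pain score is due immediately after it, so there is a natural contact well before minute 30. What is missing is an instruction to remind the provider at that contact.

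It may also be said that the interval is a drafting slip; 15 minutes after study drug, for instance, may have been meant. That is possible, but no section corrects it and staff would follow the text.

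Finally, the 30-minute limit could itself be questioned, because section 2.1 gives a duration of at least 60 to 120 minutes for intranasal fentanyl. That is a separate design decision. The prompt can be repaired without reopening it.

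**Conclusion.** The point holds from the text of 6.3 alone. On schedule the prompt has zero margin, and any infiltration delay makes the margin negative by the length of the delay. For a provider who relies on it, the reminder cannot reliably keep the patient in the primary analysis.

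The size of the loss is unknown. A reader might infer that many patients will be lost, that losses will exceed the allowance, or that the trial is underpowered. The documents give no late-start rate and leave providers free to begin sooner, so none of these follows. Nor is the sixth exclusion a cliff: 0.7997 against 0.80 is no practical difference, and 10 exclusions still leave 0.76. The tolerance of about 5 depends on two-sided alpha; with one-sided alpha it is about 15. Both figures take 49 as the total enrolled, with equal allocation, difference 2.8 and SD 3.2.

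The point should be fixed because the defect is plain, the patients at risk have already been dosed, and the remedy costs very little.

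**What to change.** First confirm the interval that was intended. Then keep the 30-minute limit and replace the prompt sentence in 6.3 with one tied to both clocks, for example: *The RA will prompt the treating provider 5 minutes after local infiltration, and in any case no later than 25 minutes after study drug administration.*

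With infiltration at minute T, the prompt falls at the earlier of T + 5 and 25:

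| Infiltration (minute) | Prompt (minute) | Margin to limit | Lidocaine time before prompt |
|---|---|---|---|
| 15 (on schedule) | 20 | 10 | 5 |
| 18 | 23 | 7 | 5 |
| 20 | 25 | 5 | 5 |
| 22 | 25 | 5 | 3 |

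At least 5 minutes always remain. For infiltration up to minute 20, the prompt still follows the lidocaine by 5 minutes. A prompt fixed only to study drug, say at minute 20, would be weaker: with infiltration at minute 22 it would come before the lidocaine. Under the proposed wording that happens only if infiltration is later than minute 25.

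The cost is one sentence and a few minutes of RA time per patient, since the RA is already there during infiltration. No extra patients are needed. The drawback is that on schedule the prompt comes 5 instead of 15 minutes after the lidocaine. The provider may still wait until minute 30 where more time for the local anaesthetic is wanted.

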6.1.4 Blinding

Research subjects, clinicians, and research personnel will be blinded.

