6.4.3.1 Primary Analyses

We will calculate the NRS scores between the two treatment arms as overall procedure pain collected at the time of dressing application. An independent group t-test will be used to assess whether the NRS scores differ between the groups. Descriptive data will be calculated for all variables. The characteristics of patients in the two groups will be compared in order to confirm adequacy of randomization. If there is unequal distribution of background variables with p values of 0.15 or less, we will include them in a multivariable analysis of the outcomes.

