6.4.3.3 Safety

Vital sign data and side-effects, including adverse events, will be obtained and recorded at 15 minute intervals after medication administration to ensure patient safety. Chi-square tests will be used to assess whether the proportion of patients with one or more side effects differs between treatment groups. The individual side effects will be described in tables. If there are marked differences between the distributions of background characteristics, a multi-variable regression will be performed to control for possible confounding.

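### Randomised, dosed patients are dropped from the analyses if incision starts more than 30 minutes after study drug, with no all-randomised or safety population to set against this

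*Combined protocol and SAP*

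**What the plan says.** The exclusion is in section 6.3 (Study Procedures), not in the statistical section: "If the I&D has not been initiated within 30 minutes of INF administration the patient will not be included in the analyses". The reason given, and the only mention of an allowance, follow directly: "due to concern for considerable tapering of INF analgesia (accounted for in sample size calculation".

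The same section sets the timetable. Study drug is given "half of total volume in each nostril) 15 minutes prior to local infiltration", and then "The RA will prompt the treating provider 15 minutes after local infiltration to ensure prompt treatment".

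Section 6.4.2 gives the sample size: "A sample size of 49 patients will support the primary outcome, based on the observed SD of 3.2", with a difference of 2.8, alpha 0.05 and power 0.8. It states no exclusion rate. Section 6.4.3.1 gives the primary test: "An independent group t-test will be used to assess whether the NRS scores differ between the groups". Section 6.4.3.3 gives the safety test: "Chi-square tests will be used to assess whether the proportion of patients with one or more side effects differs between treatment groups". Neither names an analysis population, and nothing else in section 6.4 does, so the 6.3 exclusion is the only population rule in the plan. Section 6.1.4 says "Research subjects, clinicians, and research personnel will be blinded".

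**The concern.** Time from study drug to incision is known only after randomisation and dosing. Selecting patients on it means that the t-test may no longer compare the groups that randomisation created. Sedation, nausea, a low blood pressure reading or good early pain relief could each change how soon a provider starts. If they do so differently by arm, the retained patients differ by arm too. The plan has no second analysis that would show whether the result depends on the exclusion.

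The scope is also unclear. Fading analgesia is an efficacy reason, but the rule covers the analyses without limit. Taken literally, it removes late patients from the between-arm side-effect comparison, so a patient whose early side effect delayed the incision could disappear from the comparison meant to detect such effects. It also removes their pain score after infiltration, which is scheduled at minute 15, before the cut-off is reached.

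Finally, the timetable makes late starts likely enough to matter, because the provider is prompted only when the window closes.

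**Working it through.** **Timetable (section 6.3).** Drug to infiltration is 15 minutes and infiltration to prompt is 15 minutes, so the prompt falls at 15 + 15 = 30 minutes. The limit is 30 minutes, which leaves 30 − 30 = 0 minutes. If infiltration runs late, the prompt comes after the cut-off. A provider who starts without waiting for the prompt is unaffected.

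**The plan's sample size (section 6.4.2).** Inputs: SD 3.2, difference 2.8, alpha 0.05, power 0.8. Assumed because not stated: two-sided test, 1:1 allocation, 49 as the total.

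- Normal approximation: n per arm = 2 × (1.960 + 0.842)² × (3.2/2.8)² = 20.5, so 21 per arm, 42 in total.
- Noncentral t, matching the planned test: 21.5, so 22 per arm, 44 in total (power 0.809).
- The stated inputs alone therefore do not give 49. With 10% exclusions, 44/0.90 = 48.9, which rounds up to 49. The documents do not state that 10%.
- If 49 were per arm, power would be 0.990, which does not match the stated 0.8.

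**Power under the exclusion rule**, 49 randomised, full effect of 2.8 in those retained. The excluded shares are assumptions.

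| Excluded | Analysed | Power |
|---|---|---|
| 0% | 49 | 0.851 |
| 10% | 44 | 0.809 |
| 20% | 39 | 0.758 |
| 30% | 34 | 0.696 |

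Five exclusions leave 44. A sixth leaves 43 and power 0.7997, so the implied allowance is used up at about 10%.

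**Possible bias.** If late patients' scores differ from on-time patients' by the same amount in both arms, bias = (difference between arms in excluded share) × (late minus on-time mean score). Both factors are assumptions:

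- 0.10 × 1 = 0.1 points
- 0.10 × 2 = 0.2 points
- 0.20 × 3 = 0.6 points

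The sign can go either way.

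**Cost of including everyone.** Average effect = 2.8 × (1 − late share + late share × fraction of effect kept), with all 49 analysed and SD held at 3.2.

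| Late | Effect kept | Average effect | Power | Total N for 0.80 |
|---|---|---|---|---|
| 10% | half | 2.66 | 0.813 | 48 |
| 10% | none | 2.52 | 0.770 | 54 |
| 20% | half | 2.52 | 0.770 | 54 |
| 20% | none | 2.24 | 0.670 | 68 |

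If late treated patients get no benefit, mixing them with the others also widens the spread in the fentanyl arm. Allowing for this, power is 0.756 at 10% late and 0.644 at 20%. With SD held at 3.2, inclusion and exclusion give equal power when late patients keep about 42 to 45% of the effect. Above that, inclusion has more power.

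**The case against.** The best defence is that the rule is set in advance, has a stated reason, uses a recorded clock time and is applied with patients, clinicians and research staff blinded. Differential delay has not been shown, and the illustrated bias is modest against 2.8. This stands in part: blinding does reduce the risk, and the bias inputs are assumptions. But blinding cannot stop the drug's own effects from changing when the incision starts, and the plan offers no analysis that would show whether they did.

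The bias formula also assumes the same score gap in both arms. If late fentanyl patients lose their benefit, exclusion changes the answer even when lateness is equal: with 20% late and no effect kept, the estimate is 2.8 with exclusion and 2.24 without. So 0.1 to 0.6 is an illustration, not a bound. Including everyone does change the question, from the effect within the intended window to the effect of being assigned fentanyl. The first question can still be addressed in a sensitivity analysis.

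On safety, the context suggests that only efficacy was meant. Side effects and vital signs are recorded to 120 minutes, and vital signs below threshold go to the monitors. That is fair, and one sentence would settle it, but the current text does not say so.

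No text tells providers to wait for the prompt, so the timetable shows a risk of attrition and does not by itself show bias. Lastly, the duration of at least 60 to 120 minutes in section 2.1 does not strictly contradict some tapering after 30 minutes. The two statements still pull in different directions and need explaining.

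**Conclusion.** The concern holds and should be fixed before the analysis. The plan does more than omit an intention-to-treat statement: it instructs that randomised, dosed patients be removed because of a later event, and contains nothing to offset this. Followed as written, it leaves the primary t-test without the randomised comparison, and on a literal reading the side-effect test as well.

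The size and direction of any bias are unknown, because the documents give neither an expected late share nor any difference between late and on-time patients. The assurance in section 6.3 that exclusions were allowed for is plausible, since 49 matches 44 plus about 10%. That reading depends on a two-sided test, equal arms and 49 being the total. Even if it is right, an allowance replaces lost numbers and does not restore the balance between the arms.

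**What to change.** - **Section 6.3:** replace the exclusion with: *Time from study drug to incision is recorded and does not affect inclusion in the primary or safety analyses.*
- **Section 6.4.3.1:** add: *The primary analysis includes all randomised patients in the arm assigned, regardless of time to incision. Missing pain scores at dressing application are reported by arm with reasons, and a sensitivity analysis varies them across the 0–10 range. A second sensitivity analysis is restricted to patients whose incision began within 30 minutes.*
- **Section 6.4.3.3:** add: *All patients who received study drug are included in the safety comparisons.*
- **Section 6.4.2:** state the number required (44 if the test is two-sided with equal arms), whether 49 is the total, and the rate assumed in reaching 49 and what it covers.
- **Timing:** the infiltration time, the prompt time, the 30-minute limit, the tapering rationale and the duration in section 2.1 must be reconciled by the clinical team. No timing is proposed here.

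The text changes are short. The procedural times are already recorded, and the primary score is taken at dressing application whenever the incision begins. The real cost is dilution if late patients benefit less, as set out in the second table. If lateness proves common, more than 49 patients would be needed.

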6.4 Statistical Method

6.4.1 Statistical Design

The statistical design is parallel group design with patients randomly allocated to the two treatments.

6.4.2 Sample Size Considerations

A sample size of 49 patients will support the primary outcome, based on the observed SD of 3.2, if the between group difference is no less than 2.8. This was calculated based on the following parameters: alpha = 0.05 and power = 0.8. Although smaller differences may be clinically relevant, a between-group difference of 2.8 is generally regarded as a robust difference.

We used nQuery Advisor version 7.0 (Los Angeles, CA) to calculate the sample size.

6.4.3 Planned Analyses

The planned analyses include: a comparison of the characteristics of the two treatment groups at baseline including NRS pain scores at baseline, immediately after infiltration with local anesthetic, immediately after abscess incision, overall NRS pain score throughout the procedure assessed at the time of dressing application. We will also compare the proportion of patients satisfied with treatment, comparison of proportion of providers' perception of efficacy of treatment compared to usual care, adverse events and side effects in the 120 minute period and graphical representation of pain over all time points.

